4.6.3. Safety Population

The Safety Population will consist of all patients enrolled in the study who received at least one dose of eryaspase. Safety data will be analyzed using actual dose initially received.

4.6.4. Pharmacokinetic Population

The Pharmacokinetic Population will consist of all patients with an evaluable maximum concentration (Cmax), area under the curve from time 0 to the last measurable concentration (AUC(0-t)), and Ctrough for whole blood ASNase following the first infusion. Analyses of PK data will not use any missing data imputation and will be based solely on observed data.

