6.2. Analysis of Key Pharmacokinetic Secondary Endpoints

6.2.1. Pharmacokinetic Parameter Calculations

Pharmacokinetic parameter analyses will be conducted using the Pharmacokinetic Population. The pharmacokinetic parameters to be determined are summarized below, Table 3:

Table 3 **Pharmacokinetic Parameters for Analysis**

Parameter	Description
Cmax	Maximum observed concentration after each administration
tmax	Time corresponding to occurrence of Cmax
Ctrough	Observed concentration at the end of each dosing interval
t1/2	Apparent terminal elimination half-life
AUC(0-t)	AUC from time zero to the last quantifiable concentration
AUC(0-inf)	AUC from time zero extrapolated to infinity following first administration
%AUCex	Percentage of AUC(0-inf) obtained by extrapolation following first administration
MRT	Mean Residence Time
CL	Clearance following first administration
Vss	Volume of distribution following first administration

Sponsor:	NOPHO – Nordic Society of Pediatric Hematology & Oncology		
Protocol:	NOR-GRASPALL 2016		
Document Version No.:	2.0	Document Date:	14-May-2021

PK parameters will be calculated by non-compartmental analysis (NCA) methods from the whole blood concentration-time data using Phoenix WinNonLin version 8.0 and following these guidelines:

- Actual sampling times relative to dosing rather than nominal times will be used in the calculation of all derived PK parameters.
- There will be no imputation of missing concentration data.
- Any subjects with missing concentration data will be included in the PK analysis set provided that at least Cmax and AUC(0-t) can be reliably calculated
- All below the limit of quantification (BLQ) values pre-dose will be substituted by zeros; thereafter, BLQ values between evaluable concentrations will be set to missing
- PK parameters will be estimated according to the following:
 - Cmax and Ctrough will be obtained directly from the concentration-time data.
 - tmax is the time at which Cmax is observed.
 - The terminal phase rate constant (λz) will be estimated by linear regression after log-transformation of the concentrations:
 - Only those data points that are judged to describe the terminal log-linear decline will be used in the regression.
 - A minimum number of three data points in the terminal phase will be used in calculating λz with the line of regression starting at any post-Cmax data point

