6.2.2. Pharmacokinetic Tables, Figures and Listings

Pharmacokinetic concentration data will be listed by subject including actual sampling times relative to dosing. Whole blood ASNase concentrations will be summarized by dosing course. The following descriptive statistics will be presented for concentrations obtained at each nominal time point: n, arithmetic mean, SD, coefficient of variation (CV%), median, minimum and maximum values.

Pharmacokinetic parameters will be listed by subject and summarized by course following the first and fourth infusion of the 2-week regimen. Descriptive statistics for calculated PK parameters will include n, arithmetic mean, SD, CV%, geometric mean, median, minimum, and maximum values. For t_{max}, only median, minimum, and maximum values will be presented.

Individual whole blood concentration versus actual times will be plotted by course in linear and semi-logarithmic scale. Mean and median concentrations versus nominal times will also be presented in linear and semi-logarithmic scale by course.

All concentrations below the limit of quantification (BLQ) or missing data will be labeled as such in the concentration data listings. Missing samples will be reported as no sample ("NS") and excluded from analysis. Values that are BLQ will be substituted with zero for the calculation of descriptive statistics of concentration by time point and will be displayed as "not calculable" or NC for the calculation of statistical summaries.

For graphs of arithmetic means and medians, all BLQ mean concentrations will be substituted by zeros. Any arithmetic mean or median that is BLQ will be excluded from log/linear presentation. Any BLQ values prior to the last quantifiable concentration will be plotted as zero for individual linear/linear graphs and excluded from log/linear graphs. All BLQ values after the last quantifiable concentration will be excluded from individual linear/linear and log/linear graphs.

All analyses will be based on the Pharmacokinetic Population.

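### The SAP gives two entry rules for its one PK population: section 4.6.4 requires a first-infusion trough, section 6.2.1 does not

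*SAP*

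**What the plan says.** SAP section 4.6.4 sets three conditions for the Pharmacokinetic Population, all tied to the first infusion: an evaluable Cmax, an evaluable AUC(0-t), "and Ctrough for whole blood ASNase following the first infusion". It then rules out filling gaps: "Analyses of PK data will not use any missing data imputation and will be based solely on observed data".

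SAP section 6.2.1 opens with "Pharmacokinetic parameter analyses will be conducted using the Pharmacokinetic Population". Further down it gives a different entry rule: "Any subjects with missing concentration data will be included in the PK analysis set provided that at least Cmax and AUC(0-t) can be reliably calculated". Its Table 3 defines Ctrough as "Observed concentration at the end of each dosing interval".

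SAP section 6.2.2, which covers the PK tables, figures and listings, closes with "All analyses will be based on the Pharmacokinetic Population".

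Protocol section 8.4.1 sets the sampling times. In 2-week courses the last post-dose sample is at 14 days and serves as the pre-dose sample for the next infusion. In 6-week courses the last post-dose sample is at 21 days.

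**The concern.** Two programmers working from this SAP could build two different PK datasets. They would disagree on any patient with a usable Cmax and AUC(0-t) after the first infusion but no end-of-interval value.

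Membership is fixed by the first infusion alone. Under 4.6.4 such a patient is therefore also missing from later-course output, such as the fourth-infusion summary, however complete the later profiles are.

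PK parameters are part of the primary objective in the protocol (section 3.1) and the SAP (section 2.1), although SAP section 9 moves them to secondary endpoints. Cmax and an AUC to the last quantifiable value can be calculated without a sample at the end of the interval, so 4.6.4 discards usable data from a small trial.

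**Working it through.** **1. The rules side by side**

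| First-infusion data available | SAP 4.6.4 | SAP 6.2.1 |
|---|---|---|
| Cmax, AUC(0-t) and Ctrough | in | in |
| Cmax and AUC(0-t), no Ctrough | out | in |
| Cmax or AUC(0-t) not obtainable | out | out |

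Only the middle row is in dispute. Section 6.2.1 uses the label PK analysis set, but the SAP defines no such set, and 6.2.1 itself assigns the parameter analyses to the Pharmacokinetic Population. The different label does not resolve the conflict. With imputation excluded, a missing trough cannot be supplied later.

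**2. A compliant patient in the middle row**

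- Protocol section 5.1 allows 1 to 7 eryaspase doses, and section 7.4.2 lets NOPHO ALL 2008 patients start as late as maintenance. A single dose in a 6-week course is therefore possible.
- That patient is scheduled for eight samples: pre-dose, end of infusion, 24 hours, and Days 3, 6, 10, 14 and 21.
- The interval ends at 6 × 7 = 42 days, which is 42 − 21 = 21 days after the last scheduled sample. An end-of-interval value could come only from the next pre-dose sample, and there is no next dose.
- On the Table 3 definition the patient has no Ctrough, so 4.6.4 excludes the profile and 6.2.1 keeps it.
- One limit: section 6.2.2 names parameter summaries only for the first and fourth infusions of the 2-week regimen. For this patient the loss falls mainly on the concentration summaries, plots and parameter listings.

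**3. The plan's own figures (SAP section 4.1)**

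- Inputs: 50% versus 70%, one-sided 2.5%, exact binomial test, 49 evaluable patients, about 10% dropout, 55 recruited.
- With n = 49 and success at 32 or more responders, the exact one-sided alpha is 0.0222 and the power 0.810. This agrees with the stated 80%.
- 49 / (1 − 0.10) = 54.4, rounded up to 55. This agrees with the stated 55.

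SAP sections 4.6.1 and 6.1 place the primary test, and 4.6.1 the key secondary test, in the Evaluable Patients population. None of these figures depends on the PK population.

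**4. How many patients could be affected**

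The documents give no count for the middle row. The only related figure is the dropout allowance:

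- 55 − 49 = 6 patients, and 6 / 55 = 10.9%.
- If all 6 lack the trough but have Cmax and AUC(0-t), the PK population is 49 under 4.6.4 and 55 under 6.2.1.
- If all 6 also lack Cmax or AUC(0-t), both rules exclude them and the difference is 0.

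Within the planned allowance the range is therefore 0 to 6 of 55.

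**The case against.** **The effect is confined to descriptive output.** This stands. No test, alpha, power or sample size changes. SAP section 4.11 also puts all available data into by-subject listings, so the excluded values should remain visible somewhere.

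**Requiring a trough has a purpose.** AUC(0-t) runs to the last quantifiable concentration. Without an end-of-interval sample it may stop at Day 10 or earlier in a 2-week course, and pooling it with AUC to Day 14 mixes intervals and tends to lower the mean. Adding Ctrough to 6.2.1 would reconcile the text equally well. This stands as a cost of the fix, but it concerns AUC(0-t) and is no reason to discard the same patient's Cmax or later courses.

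**Day 14 may be meant as the trough.** SAP section 2.1 equates Ctrough with the nadir, and section 2.3 attaches that word to Day 14 after the first infusion. On that reading the 6-week patient qualifies. Table 3 says otherwise, so the 6-week exclusion holds only on the Table 3 definition. The basic mismatch between 4.6.4 and 6.2.1 does not depend on it.

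**Two stronger readings are tempting, and the documents support neither.**

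- *A trough below quantification is treated as missing, so patients who lost activity are removed.* A reader might infer this from "BLQ values between evaluable concentrations will be set to missing". The first half of that sentence sets pre-dose values below quantification to zero. Protocol section 8.4.1 makes the Day-14 sample the next pre-dose sample in 2-week courses. Section 6.2.2 works by course, so the trough is the last point of its own profile and does not lie between two quantifiable ones.
- *Requiring a trough favours patients who kept activity.* The condition turns on having a sample, not on its level. Protocol section 7.6 stops eryaspase for allergy or absent activity, so a link with missed sampling is conceivable. However, the Day-14 sample belongs to the course already given, and section 11.1 keeps patients who stop for toxicity or lack of activity under monitoring for a month and asks them to continue assessments. No data on reasons for missing troughs are given.

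**Conclusion.** The conflict is real: the SAP has one PK population and two incompatible entry rules for it. Following 4.6.4 drops patients with a usable first-infusion profile but no end-of-interval value from all section 6.2 PK summaries, later courses included. On the Table 3 definition of Ctrough, it also drops a compliant patient given a single dose in a 6-week course.

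The size is unknown. The 0 to 6 of 55 range assumes that missing troughs stay within the SAP's dropout allowance; 6 is a ceiling under that assumption, not an expected number. The direction of any bias is not established. The point is minor, because it affects descriptive PK results and not the primary or key secondary test.

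**What to change.** Delete the Ctrough condition from SAP section 4.6.4 so that it matches 6.2.1. State that each PK parameter is summarised over all patients with an available value, and report n for each parameter. Use the same name for the population in both sections.

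The change is one deleted phrase and one or two added sentences. It needs no new data and does not touch the primary analysis. It has two costs:

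- n will differ between parameters.
- AUC(0-t) may cover a shorter interval in patients without an end-of-interval sample. Report the last sampling time with AUC(0-t), or show AUC(0-t) separately for patients with a full interval.

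If the sponsor prefers to keep the trough condition for comparability, 6.2.1 must be changed to match and the patients lost must be counted. That also removes the contradiction, but it gives up usable data.

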4.7. Adjustments for Covariates

No formal statistical analysis that adjusts for possible covariate effects is planned.

4.8. Multiple Comparisons/Multiplicity

Multiplicity is not of concern for this study given the design and objectives of this study.

4.9. Subpopulations

NA

4.10. Withdrawals, Dropouts, Loss to Follow-up

Subjects who withdrew from the study will not be replaced.

4.11. Missing, Unused, and Spurious Data

In general, there will be no substitutions made to accommodate missing data points. All data recorded on the CRF will be included in data listings that will accompany the clinical study report. General missing values and completely missing dates will not be replaced. For incomplete dates, when day and month are missing, the date will be considered as missing. When the day is the only missing date, it will be replaced by the 15th of the month of event. If there are discrepancies with the estimated date using this general rule with other available source data, then another rule will be used.

Sponsor:	NOPHO – Nordic Society of Pediatric Hematology & Oncology		
Protocol:	NOR-GRASPALL 2016		
Document Version No.:	2.0	Document Date:	14-May-2021

No other data imputation will be applied for missing values during the treatment phase. All available data for all patients will be presented in by-subject listings.

When deriving all other variables that use dates, for dates that include missing values, the following conventions in Table 2 will be used.

Table 2 Convention for Imputation

Value	Imputation
Missing day, month, and year	Not imputed
Missing day and month	Day imputed to June 30th
Missing day	Day imputed to the 15th

When using dates from drug administration pages for the purposes of deriving treatment exposure, the following conventions will apply:

- If the start date is missing, it will be assumed that the first drug intake was given at the date of consent/assent. This date will replace all first administration missing dates.
- If the last administration date is missing, the date will be imputed with the date taken from the “Status of the Patient at the End of the Treatment” eCRF page (Date of last treatment) or if missing, with the date of last contact taken from the “Status of the Patient” eCRF page.

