7.4.3 Dispensing/Allocation of ERYASPASE

Once a patient has consented and is determined to be eligible for this study, ERYTECH Pharma must be notified and the process below followed:

To initiate eryaspase manufacturing and allocation of eryaspase, NOPHO or designee must be provided with the documents listed below:

- **At Screening:** a validated phenotype and ABO status (double determination is mandatory), as well as IAST results are required. The blood group form should be completed, and the lab results should be attached to this form. A template of the blood group form along with instructions is available in IMP Manual.
- **5 working days prior to each eryaspase injection:** Prescription Sheet indicating patient identifiers, weight, and estimated time of delivery. A template of the prescription sheet is available in IMP Manual.

- **Within 72 hours of each eryaspase injection:** Documentation of the IAST (Irregular Antibody Screening Test) performed at the local immuno-hematology laboratory.
- **In case of positive IAST** or previous history of positivity, a compatibility test is mandatory in order to appropriately select the packed Red Blood Cells. In cases of a positive IAST where compatibility testing is required, the administration of eryaspase may be delayed depending on the timeline for the compatibility results.

Instructions for blood sampling management sent to French blood bank (EFS) for selecting compatible packed Red Blood Cells are detailed in IMP Manual.

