- **CAUTION: If a bag of eryaspase is partially transfused or not transfused to the patient, this must be documented accordingly with full explanation of why transfusion was incomplete or not done. This information is documented on the Shipment and Administration Form and within the patient's chart.**

Post Administration

The responsible person of administration should record on "Shipment and Administration Form" the below information after completion of administration:

- Date and duration of administration (start and stop time)
- Name and position, signature
- Whether the entire content was administered and the lines accurately rinsed, with full explanation if it was not the case.

The completed document should be sent immediately following infusion to Erytech to confirm eryaspase administration. Please refer to the IMP Manual for instructions.

7.4.5 The monitoring during and immediately after the infusion of IMP. The patient must remain awake and should be constantly under medical supervision **during the administration and for at least one hour after the end of administration** for occurrence of any adverse reactions. The infusion must be stopped **immediately in case of occurrence of any adverse reactions and the PI (or designee) must be informed.**

Eryaspase administration should be performed **under medical responsibility** and only by trained staff. The staff must be trained in handling blood products and in diagnosing and treatment of acute allergic reactions. Medication and equipment to treat acute allergic reactions in relation to infusion must be placed in the room of administration and the personnel must have immediate access.

The management of adverse reactions should be based on clinical presentation and is at investigator's discretion. Should the patient exhibit symptoms suggestive of hypersensitivity reactions to eryaspase, the general treatment of such reactions will follow the guidelines of the department.

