11.0 DISCONTINUATION

11.1 Early Discontinuation of Study Drug

A patient may be discontinued from study treatment at any time if the patient, the investigator, or the Sponsor feels that it is not in the subject's best interest to continue. The following is a list of possible reasons for study treatment discontinuation:

Lack of asparaginase activity (in scheduled blood samples after a dose of eryaspase)

Disease progression

Subject withdrawal of consent (or assent)

Subject is not compliant with study procedures as judged by the investigator and/or sponsor

Adverse event that in the opinion of the investigator would be in the best interest of the subject to discontinue study treatment

Lost to follow-up

Sponsor and/or Erytech request for early termination of study

Patients who stop treatments from the study for toxicity or lack of activity will continue to be monitored for 1 month after last administration of eryaspase for safety follow up.

In addition, the patient will be requested to continue assessments until 1-year maintenance follow up.

In case of early withdrawal, the reason and the date of withdrawal must be documented in the patient's medical chart as well as in the study CRF.

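### SAP 4.11 dates a missing first infusion at consent, which the protocol's ordering lead time rules out, and its last-resort date for a missing final infusion can also overstate exposure

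*SAP*

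**What the plan says.** SAP 4.11 has a short set of rules for dates on the drug administration pages, limited to the derivation of treatment exposure.

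- First infusion: "If the start date is missing, it will be assumed that the first drug intake was given at the date of consent/assent". The rule covers every missing first-administration date.
- Last infusion, step 1: "If the last administration date is missing, the date will be imputed with the date taken from the" end-of-treatment status page of the eCRF, where a date of last treatment is recorded.
- Last infusion, step 2: "or if missing, with the date of last contact taken from the" patient-status page.

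The same section has two rules for a date that lacks both day and month. The general text says that "when day and month are missing, the date will be considered as missing". Table 2, introduced as applying to all other variables that use dates, has "Day imputed to June 30th".

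The imputed dates feed treatment duration (SAP 7.2: last minus first injection date, plus 1, divided by 30.4375) and the exposure period (SAP 4.2: from first dose to 30 days after the last dose, or to relapse or death if earlier).

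On timing, Protocol 7.4.3 has manufacture begin once the patient has consented and is found eligible, with the prescription sheet due "5 working days prior to each eryaspase injection". Protocol 7.4.4 has the date and the start and stop times of each infusion written on the Shipment and Administration Form, and adds: "The completed document should be sent immediately following infusion to Erytech to confirm eryaspase administration".

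**The concern.** An imputed date should be one the patient could actually have had. The consent date fails this test for anyone treated per protocol, because the product has yet to be ordered on that day. The error also has a fixed direction: the start can only be too early, so duration can only be too long.

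The second fallback for the last infusion has the same direction. Follow-up runs well past the last dose. Protocol 8.1 keeps patients under observation for at least one month and then for up to one year in maintenance, and for patients who stop early Protocol 11.1 says: "In addition, the patient will be requested to continue assessments until 1-year maintenance follow up". Last contact is therefore a poor stand-in for last dose.

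At stake are the treatment-duration summary and the exposure-period dates. Both are descriptive.

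**Working it through.** **Inputs.** Treatment-duration formula: SAP 7.2. Dose schedules: Protocol 7.4.2 and synopsis. Lead time of 5 working days: Protocol 7.4.3. Follow-up of at least 1 month and up to 1 year: Protocol 8.1 and 11.1. Time on study of about 1.5 years: synopsis.

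**Step 1: reproduce the plan's own figures.** Take four doses two weeks apart, then three at 6-week intervals, with the first 6-week interval counted from dose 4. The doses fall on days 1, 15, 29, 43, 85, 127 and 169. Duration is 169/30.4375 = 5.55 months, or (169 + 30)/30.4375 = 6.54 months with the 30-day tail. Both fit the stated figure of about 6 months. Time on study is 8 + 169 + 365 = 542 days, and 542/365.25 = 1.48 years, against the stated 1.5.

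Seven two-weekly doses end on day 1 + 6 × 14 = 85, so duration is 85/30.4375 = 2.79 months.

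**Step 2: error in the first date.** Counting back 5 working days from an infusion on any weekday gives 7 calendar days, ignoring public holidays. With consent and ordering on the same day, which is the shortest case, the imputed start is 7 days early. Protocol 9.1 puts screening at least 8 days before treatment, while the synopsis says up to 8 days. Those two statements need reconciling, but the lead time gives the 7-day minimum under either.

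- Single infusion, start 7 days early: true 1 day; imputed 7 + 1 = 8 days.
- Seven doses, NOPHO schedule: 176/30.4375 = 5.78 months (7 days early) or 177/30.4375 = 5.82 months (8 days early), against 5.55. At 8 days the excess is 8/169 = 4.7%.
- Seven two-weekly doses: 92/30.4375 = 3.02 or 93/30.4375 = 3.06 months, against 2.79. At 8 days the excess is 8/85 = 9.4%.

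The single-infusion error needs only the consent rule and a correctly recorded date of last treatment.

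**Step 3: error in the last date, only if both the administration date and the date of last treatment are blank.**

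| Schedule (7 doses) | True | Last contact 30 days after last dose | Last contact 365 days after last dose |
|---|---|---|---|
| NOPHO ALL 2008 | 5.55 months | 199/30.4375 = 6.54 | 534/30.4375 = 17.54 |
| Two-weekly | 2.79 months | 115/30.4375 = 3.78 | 450/30.4375 = 14.78 |

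One year is an approximate upper figure. If last contact fell at 1.5 years (about 548 days), the excess would be 548 − 169 = 379 days or 548 − 85 = 463 days.

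**The case against.** The strongest reply is that these rules may never be used. Every infusion date is recorded at the bedside and sent to the manufacturer, missing CRF data are queried (Protocol 13.1), validation checks are run (13.3), and drug accountability is monitored (7.5, 13.6.2). Neither document suggests how many dates will be missing. This stands as a limit on the number of patients affected. It does not make the consent rule correct, and it shows that a better source exists.

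Four stronger readings are tempting, and the documents do not support them.

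- **That a missing last date is simply set to last contact.** The recorded date of last treatment comes first. An error of a month to a year needs two separate fields to be blank for the same patient.
- **That adverse events would be wrongly counted as treatment-emergent.** SAP 4.11 limits these rules to exposure, and neither SAP 4.11.2 nor 8.1 says that imputed dose dates set the treatment period. Protocol 4.4 collects events only from start of treatment to 30 days after the last dose. SAP 8.1 describes a wider window starting at consent, so the possibility is not excluded, but it is not established.
- **That the primary or key secondary result is biased.** Missing asparaginase activity is not imputed (SAP 4.11.1). Dose intensity and compliance (SAP 7.1, 7.3) use doses and infusion counts, not dates.
- **That the two partial-date rules contradict each other outright.** Table 2 is worded for other variables, so the two rules have different scopes. What is missing is a statement of where one ends and the other begins.

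**Conclusion.** The consent-date rule is wrong as written, in a known direction. For a patient treated per protocol it places the first infusion at least about 7 calendar days too early. This turns a 1-day duration into about 8 days, and at an 8-day gap it lengthens a seven-dose duration by about 5% (NOPHO schedule) or 9% (two-weekly). The last-contact fallback can add about 1 month to about 1 year to treatment duration, but only when the recorded date of last treatment is also blank. It can also push back the end of the exposure period, unless relapse or death closes that period first.

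The figures assume a weekday infusion, adherence to the ordering rule, consent no later than the order, and follow-up as planned. The number of patients affected is not given and is probably small. The consequence is confined to descriptive exposure summaries. This is a minor point, worth correcting because the rule is demonstrably wrong and the remedy is cheap.

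**What to change.** In SAP 4.11:

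1. Recover any missing infusion date from the Shipment and Administration Form.
2. If a last date is still missing, use the recorded date of last treatment, then the latest documented infusion.
3. If a first date cannot be recovered, leave it missing.
4. Delete the consent-date and last-contact imputations.
5. State which variables fall under the rule that treats a date without day and month as missing, and which fall under the June 30th rule in Table 2.

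The cost is a change of SAP wording and a small look-up in a record the trial already keeps. A few durations may end up missing, and the latest documented infusion may understate duration if a later dose went unrecorded. Marking such dates in the listing would let a reader see how often this arises.
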